4.2.3 End of Study

The end of the study is defined as the date of the last visit of the last participant in the study.

4.2.4 Baseline

Baseline is defined as the last non-missing measurement prior to the date and time of the dose of study intervention.

For the exploratory analysis using TLFB, baseline is the mean alcohol level as measured on Day -1.

No imputation will be done for missing baseline value for derivation of change from baseline or summary tables and shift tables.

4.2.5 Controlled, Repeat, Retest, Scheduled and Unscheduled Assessment

Repeat, retest, and unscheduled assessment will not be considered for the calculation of summary statistics and figures, unless assessment qualifies as baseline.

Average of controlled and planned (scheduled) assessment will be considered for the calculation of summary statistics and figures, if more than one controlled/planned assessment will be performed at a specific time point.

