7.3.3. Electrocardiogram Findings

If a clinically significant finding is identified (including, but not limited to, the QTcF findings below) after enrollment, the Investigator or qualified designee will determine if the participant can continue in the study and if any change in participant management is needed. This review of the ECG printed at the time of collection must be documented. Any new clinically relevant finding should be reported as an AE.

- Absolute QTcF > 500 msec and/or
- QTcF change of > 60 msec from baseline and >450 msec.
- New and clinically significant arrhythmia or rhythm abnormality.

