9.4.1. General Considerations

In general, summary statistics (n, mean, SD, median, minimum, and maximum for continuous variables, and number and percentage of participants in each category for categorical variables) will be provided for all variables.

Baseline is defined as the last non-missing measurement prior to the date and time of the dose of study intervention.

All analyses will be based on observed data without imputation for missing values. Except for outlier analyses, measurements collected from unscheduled visits will not be included in the summary tables or figures but will be included in the participant listings. Source data for the summary tables and statistical analyses will be presented as participant data listings.

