Monitoring:	
If ALT or AST $\geq 3 \times \text{ULN}$ AND total bilirubin $\geq 2 \times \text{ULN}$ or INR > 1.5:
 
 Repeat liver function tests (include ALT, AST, alkaline phosphatase, total bilirubin, and INR) and perform liver function follow-up assessments within 24 hours. Monitor participant twice weekly until liver function test abnormalities resolve, stabilize, or return to baseline. A specialist or hepatology consultation is recommended. 
If ALT or AST $\geq 3 \times \text{ULN}$ AND total bilirubin $< 2 \times \text{ULN}$ and INR ≤ 1.5:
 
 Perform liver function tests (include ALT, AST, alkaline phosphatase, total bilirubin, and INR) and perform liver function follow-up assessments within 24 to 72 hours Monitor participants weekly until liver function abnormalities resolve, stabilize, or return to baseline

Follow-Up Assessments:

- Viral hepatitis serology (includes Hepatitis A IgM antibody; HBsAg and HBcAb; hepatitis C RNA; cytomegalovirus IgM antibody; Epstein-Barr viral capsid antigen IgM antibody [or if unavailable, heterophile antibody or monospot testing]; and hepatitis E IgM antibody)
- Obtain serum CK, LDH, GGT, GLDH, and serum albumin
- Fractionate bilirubin, if total bilirubin $\geq 2 \times \text{ULN}$
- Obtain complete blood count with differential to assess eosinophilia
- Record the appearance or worsening of clinical symptoms of liver injury, or hypersensitivity, on the eCRF
- Record use of concomitant medications or ingestions (including wild mushrooms, acetaminophen, herbal remedies, recreational drugs, and other over-the-counter medications). Note any concomitant medications that have been recently initiated or for which doses have increased.
- Record alcohol use on the eCRF

If ALT or AST $\geq 3 \times \text{ULN}$ AND total bilirubin $\geq 2 \times \text{ULN}$ or INR > 1.5 obtain the following in addition to the assessments listed above:

- Anti-nuclear antibody, anti-smooth muscle antibody, Type 1 anti-liver kidney microsomal antibodies, and quantitative total immunoglobulin G (IgG) or gamma globulins
- Liver imaging (ultrasound, magnetic resonance, or computerized tomography) and/or liver biopsy to evaluate liver disease
- Liver biopsy may be considered and discussed with local specialists if available, for instance:
 - When serology raises the possibility of autoimmune hepatitis (AIH)

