4.13.1 Adverse Events

All outputs for AEs/treatment-emergent adverse events (TEAEs) will be based on the SP unless specified separately in TLF shells. Describe the AE dictionary including version that is to be used to classify the AEs.

All AE summaries should provide the number and percentages of participants reporting at least one AE and the total number of events reported.

Summaries of AEs will include the following:

- Incidence of AEs - Overview (by treatment and overall)
- Incidence of TEAEs (by treatment and overall, SOC, and PT)
- Incidence of TEAEs by maximum relationship (by treatment and overall, SOC, and PT)

- Incidence of TEAEs by maximum severity (mild/moderate/severe, by treatment and overall, SOC, and PT)

Summary tables will contain counts of participants, percentages of participants in parentheses, and the number of events where applicable. A participant who has multiple events in the same SOC and PT will be counted only once in the participant counts, but all events will be included.

All Adverse Events (AEs)

All AEs will be listed including pretreatment AEs.

Treatment-emergent Adverse Event

A TEAE will be defined as any AE that emerges during treatment (i.e., AE which started after study drug administration or pre-existed that worsened in severity after study drug administration) and those will be analyzed for the purpose of safety analysis.

TEAEs will be summarized by SOC and PT, including the number and percentage of participants experiencing events, separately.

Severity

TEAEs will be summarized by SOC, PT, and severity, including the number and percentage of participants experiencing events. If a participant reports the same TEAE more than once within that SOC and PT, the TEAE with the highest severity will be used in the corresponding severity summaries.

The summaries including severity will be reported by Common Terminology Criteria for Adverse Events (CTCAE) grade presented as below.

- Grade 1: Mild;
- Grade 2: Moderate;
- Grade 3: Severe or medically significant but not immediately life-threatening;
- Grade 4: Life-threatening consequences;
- Grade 5: Death related to AE.

participants who experience the same event multiple times will be included in the most severe category. Events with missing intensity will be considered as 'Grade 3' events for summary purposes but recorded as missing in the listings.

Relationship (Causality)

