Laboratory abnormalities that are considered clinically significant (CS) are recorded in the database as AEs. Therefore, no tabulation of laboratory values meeting any CS criteria (except liver chemistry) will be presented as all relevant information will be presented in the AE summaries.

Results of pregnancy tests (females only), serology, drugs of abuse and alcohol tests will be listed only.

4.13.4 Vital Signs,

Temperature (by skin refraction), pulse rate, respiratory rate, and blood pressure will be assessed.

Blood pressure and pulse measurements will be assessed in the seated position with a completely automated device. Heart rate will be measured using telemetry during EIAs. Manual techniques will be used only if an automated device is not available. Blood pressure and pulse measurements should be preceded by at least 5 minutes of rest for the participant in a quiet setting without distractions (e.g., television, cell phones).

Temperature will be obtained in degrees Celsius (°C), pulse rate will be counted for a full minute and recorded in beats per minute, and respirations will be counted for a full minute and recorded in breaths per minute.

Vital signs data will be listed by participant including changes from baseline. Vital signs will be summarized in tabular format to include descriptive statistics (n, mean, SD, median, minimum, maximum) for absolute values and changes from baseline will be presented by treatment, and placebo and time-point.

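### SAP 4.2.5 omits the protocol's outlier-analysis exemption, so liver-test and QTcF peaks seen only at repeat or unscheduled assessments enter no specified by-arm summary of values

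*SAP*

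**What the plan says.** Protocol 9.4.1 sets the general rule: "Except for outlier analyses, measurements collected from unscheduled visits will not be included in the summary tables or figures". Such values go to the participant listings. The protocol names outlier analyses here without defining one; Protocol 9.4 leaves technical detail to the SAP.

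SAP 4.2.5 gives its own rule: "Repeat, retest, and unscheduled assessment will not be considered for the calculation of summary statistics and figures, unless assessment qualifies as baseline". Its only exception is a value that serves as baseline. SAP 4.21, on changes to the planned analysis, is marked as not applicable.

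For laboratory data, SAP 4.13.3 plans by-arm descriptive statistics by time point, including minimum and maximum, and low/normal/high shift tables for haematology and biochemistry. Screening and end-of-study values are left out of the shift tables. It then says "Laboratory abnormalities that are considered clinically significant (CS) are recorded in the database as AEs" and concludes "Therefore, no tabulation of laboratory values meeting any CS criteria (except liver chemistry) will be presented". No criteria, layout, arm split or rule on unscheduled values is given for the liver exception.

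For ECG, SAP 4.13.5 plans descriptive statistics by treatment and a separate listing of abnormalities. It specifies no categorical or worst-value QTcF table.

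**The concern.** Laboratory tests and 12-lead ECG are primary endpoints (Protocol 9.4.2, SAP 3.2.1). With 12 active and 4 placebo participants, means say little about uncommon safety events, and the information lies mostly in the extremes.

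The protocol itself produces off-schedule values. Protocol 8.2.6 has clinically significant laboratory results repeated until they normalise or stabilise. Protocol 10.6 calls for repeat liver tests after ALT or AST reaches 3×ULN and, in the more severe pattern, "Monitor participant twice weekly until liver function test abnormalities resolve, stabilize, or return to baseline". A rising liver signal can therefore peak at a draw that SAP 4.2.5 bars from summary. A bilirubin or INR elevation that accompanies it may also appear only on the repeat. The by-arm table of values would then show the lower scheduled result, with the peak visible only in a listing.

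**Working it through.** The documents state no figure to reproduce, so the check compares the texts and traces each kind of value to its output.

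**1. The two exclusion rules**
- Protocol 9.4.1: covers unscheduled visits; exempts outlier analyses.
- SAP 4.2.5: covers repeat, retest and unscheduled assessments; exempts baseline values only.
- Difference: the SAP excludes more and lacks the outlier exemption. The SAP text defines no outlier, worst-post-baseline or threshold-count analysis. A term for potentially clinically significant values is in its abbreviation list but is not used in any planned analysis.

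**2. Where off-schedule values arise**
- Liver: Protocol 10.6 requires repeats within 24 hours and then twice weekly if ALT or AST is ≥3×ULN with total bilirubin ≥2×ULN or INR >1.5. Without those accompanying findings, repeats are due within 24 to 72 hours and then weekly. Protocol 8.2.6 adds repeats of any clinically significant laboratory result.
- QTcF: Protocol 7.3.3 sets review criteria of an absolute value >500 msec, or "QTcF change of > 60 msec from baseline and >450 msec". Neither 7.3.3 nor 8.2.4 fixes a timetable for repeat ECGs, so an unscheduled QTcF peak is possible but not built into the plan.

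**3. Where each value goes under the SAP**
- Liver-test or QTcF peak at a scheduled assessment: enters the by-arm descriptive table and is visible as the maximum (SAP 4.2.6, 4.13.3, 4.13.5).
- Liver-test peak at a repeat or unscheduled draw: barred from summary statistics. It can reach a by-arm table only as an AE term, or through the undefined liver exception in 4.13.3, to which 4.2.5 applies as written.
- QTcF peak at a repeat or unscheduled ECG: barred. It can reach a by-arm table only as an AE term, and there is no counterpart to the liver exception.
- Count of participants meeting the 7.3.3 QTcF criteria: none specified by arm, whether the ECG was scheduled or not.
- Shift tables: any value above the reference range is classed as high, so they do not separate multiples of ULN.

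**4. Size**
- Assume four weeks of liver follow-up; the protocol sets no duration.
- Weekly: 1 × 4 = 4 results. Twice weekly: 2 × 4 = 8 results. Summarised under 4.2.5: 0.
- Illustration with invented values: ALT of 3.2×ULN at a scheduled draw and 6×ULN on the repeat gives a tabulated maximum of 3.2×ULN. Both values pass 3×ULN, so a count at that cut would not change. What is lost is the peak itself and any bilirubin ≥2×ULN or INR >1.5 first seen on the repeat.
- One participant is 1/12 = 8.3% of the active arm or 1/4 = 25% of the placebo arm, so one missed concurrent pattern visibly changes a by-arm count.

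**The case against.** The strongest reply has five parts.

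- **No promised analysis was cancelled.** Protocol 9.4.1 mentions outlier analyses only as an exception, and the primary safety analysis in 9.4.2 lists none. This stands. The defect is that the exemption is not carried over, a difference that SAP 4.21 does not record.
- **Clinically significant findings are covered by the AE route.** SAP 4.13.3 says so, Protocol 7.3.3 does the same for new clinically relevant ECG findings, and SAP 4.13.1 plans "Incidence of TEAEs (by treatment and overall, SOC, and PT" as well as a table by maximum severity. This route does not depend on whether the draw was scheduled. It stands for events. It does not supply the value or show the concurrent ALT/AST with bilirubin or INR pattern, and it depends on the investigator's judgement of significance.
- **A liver tabulation is retained.** True, but it is undefined, and nothing in 4.13.3 exempts it from 4.2.5.
- **The QTcF criteria in 7.3.3 trigger investigator review and are not table categories.** True. They are still the only post-enrolment QTcF cuts that the protocol sets, and so the natural ones to count.
- **Listings suffice for 16 participants, and the TLF shells are not available here.** Both points lower the stakes. A shell may already contain such a table, but the SAP text neither specifies one nor permits unscheduled values in it.

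A reader might infer that peak liver and QTcF values reach no by-arm table at all. The documents do not support that, because scheduled peaks appear as by-arm maxima and clinically significant findings appear as TEAEs.

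**Conclusion.** The point holds for liver-test and QTcF peaks seen only at repeat, retest or unscheduled assessments. No by-arm summary of values specified in the SAP would contain them, and the one tabulation that might, for liver chemistry, is undefined. The liver part carries more weight in practice because the protocol mandates off-schedule testing. For QTcF the gap in the text is clearer, since there is no exception, but an off-schedule peak is less certain to arise.

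The effect is on what the by-arm safety tables show for a primary endpoint. It does not follow that safety signals would go undetected: the stopping and review rules act on the values themselves, and laboratory and ECG results are listed by participant. The count of 4 to 8 unsummarised results rests on the assumed four weeks of follow-up. The conclusion also assumes that 4.2.5 is applied as written and that no TLF shell overrides it. The correction is worth making because it is cheap and removes an undeclared difference from the protocol.

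**What to change.** - **SAP 4.2.5:** add an exception for outlier (worst post-baseline) analyses, which use all post-baseline values, scheduled or not.
- **SAP 4.13.3:** define the liver-chemistry tabulation by arm on worst post-baseline values, with the categories already in Protocol 10.6: ALT or AST ≥3×ULN, total bilirubin ≥2×ULN, INR >1.5, and their concurrent combination. Show the maximum value beside the counts. The expedited-report line of 10.6 uses >2×ULN for ALT or AST where its footnote b and monitoring rows use ≥3×ULN; those passages must be reconciled before the concurrent category is fixed.
- **SAP 4.13.5:** add a by-arm worst-value QTcF count on the Protocol 7.3.3 criteria: >500 msec, and change >60 msec with a value >450 msec.
- **By-visit summaries:** leave on scheduled values.

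Since the SAP is final, SAP section 1 provides a Statistical Method Modification Form for the change. If the sponsor prefers to keep 4.2.5 as it is, the departure from Protocol 9.4.1 should be recorded in 4.21 and the liver tabulation still defined.

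The cost is one sentence and two small tables. The extremes may look slightly less favourable. No further data collection is needed.

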4.2.6 Summary and Representation of Data

Continuous data will be summarized in terms of mean, standard deviation (SD), median, minimum, maximum, and number of observations, unless otherwise stated.

Categorical data will be summarized in terms of the number of participants providing data at the relevant time point (n), frequency counts, and percentages.

The minimum and maximum will be reported to the same number of decimal places as the raw data recorded in the database. The mean and median will be reported to one more decimal place than the raw data recorded in the database. The SD will be reported to two more decimal places than the raw data recorded in the database. In general, the maximum number of decimal places reported shall be four for any summary statistics.

Percentages will be presented to one decimal place. Percentages will not be presented for zero counts. Percentages will be calculated using N as the denominator. If sample sizes are small, the data displays will show the percentages, but any textual report will describe frequencies only. Percentage will be presented as whole number if count is 100.

If for any summary table, n is less than three then only n, minimum, and maximum should be presented, and other summary statistics will be left blank.

4.2.7 On-treatment assessment/event

The overall observation period will be divided into three mutually exclusive segments:

1. **screening period:** from day of participant's informed consent to before date of first administration of study treatment
2. **dosing period:** from date of first administration of study treatment to 58 days after date of last administration of study treatment (including start and stop date)
3. **follow-up period:** starting at day 58+1 after last administration of study treatment.

4.3 Software

All report outputs will be produced using SAS® version 9.4 or later in a secure and validated environment.

The PK analyses will be conducted using Phoenix® WinNonlin (WNL) version 8.3 or later in a secure and validated environment.

All report outputs will be provided to the Sponsor in RTF format.

4.4 Study Participants

4.4.1 Analysis Populations

Enrolled Population (ENR): All participants who sign the ICF.

Randomized Population (RP): All participants who sign the ICF and who are randomized to study intervention.

Safety Population (SP): All participants randomized to study intervention and who receive at least 1 dose of DCR-AUD or placebo. Participants will be analyzed according to the initial dose received.

Pharmacokinetic Population (PKP): All participants randomized to study intervention and who receive at least 1 dose of DCR-AUD and have at least 1 postdose PK assessment.

Pharmacodynamic Population (PP): All participants randomized to study intervention and who

receive at least 1 dose of DCR-AUD or placebo and have at least 1 postdose PD assessment.

A summary table with the number of participants in each of the analysis population will be provided and this table will be displayed by treatment/sequence and overall, for ENR. A listing of participants excluded from analysis populations will also be provided including reason of exclusion for ENR.

4.4.2 Disposition of Participants

A clear accounting of the disposition of all participants who enter the study will be provided from screening (excluding screen failure data) to study completion.

A summary of participant study completion status and reason for study withdrawal will be provided for the ENR. This display will show the number and percentage of participants who withdrew from the study, including primary reasons for study withdrawal.

A by-participant listing of study discontinuation will be presented for the ENR. The listing will include dose date and reasons for study discontinuation.

A randomization listing will be presented and include the following: each participant's randomization number, the treatment to which the participant has been randomized and replacement randomization number (if any) for the RP.

4.4.3 Protocol Deviations

All protocol deviations are predefined in the separate document, Protocol Deviation Assessment Plan.

4.4.3.1 Protocol Deviations with Non-PK Implications

The defined protocol deviations will be collected during the study period by site monitor/clinical team and programming team. All deviations related to study inclusion or exclusion criteria, conduct of the study, participant management or participant assessment, and handling of the participant's rights will be described.

A summary table of important protocol deviations by study day, and treatment arm will also be provided for RP.

4.4.3.2 Protocol Deviations with PK Implications

Protocol deviations that may potentially impact PK parameter derivations include, but are not limited to:

- SC administration deviations – interruption of administration, etc.
- Missed PK samples that impact estimation of PK parameter(s)
- Concomitant medications not authorized by protocol
- PK samples obtained out of allowance window that may impact the estimation of PK parameter(s)

Protocol deviations (mentioned in Sections 4.4.3.1 and 4.4.3.2) and analysis populations will be reviewed in the blinded Data Review Report (DRR) Meeting to decide inclusion or exclusion of

participant(s) from analyses populations. Decisions regarding the exclusion of participants and/or participant data from analyses will be made prior to database lock and will be documented and approved.

A by-participant- listing of important and not-important protocol deviations will be provided including participant identifier; exclusion from specific analysis sets; and protocol deviation classification, and protocol deviation description and exclusion from specific analysis populations. Protocol Deviations related to COVID-19 will be listed separately.

4.5 Demographics and Baseline Characteristics

Demographic and anthropometric variables (age, sex, ethnicity, race, height, weight, and BMI) will be listed by participant. Demographic characteristics (age, sex, ethnicity, and race) and anthropometric characteristics (height, weight, and BMI) will be summarized by treatment, placebo, and overall, for the SP.

A by-participant listing for substance use will be provided for the SP.

